## Grading Scales for the Assessment of Severity for Solicited Injection-Site AEs, Solicited Systemic AEs, Elevated Temperature, and AESI

**Note:** Injection-site redness/erythema and injection-site swelling reported from Days 1 through 5 postdose will be evaluated by maximum size.

PRODUCT: MK-1654

PROTOCOL/AMENDMENT NO.: 004-05

 Table 13
 Solicited Injection-site AE Severity Grading Scale

Solicited Injection-	Severity Grade					
Site AE a	Grade 1	Grade 2	Grade 3	Grade 4		
Pain/Tenderness	Mild pain or tenderness with or without associated symptoms; does not interfere with normal activity	Moderate pain or tenderness. Interferes with normal activity	Severe pain or tenderness; prevents normal activity	Life-threatening consequences; urgent intervention indicated		
Erythema/Redness	Size measured as >0 and ≤1	Size measured as >1 and ≤2	Size measured as >2	Necrosis or exfoliative dermatitis OR results in ER visit or hospitalization		
Swelling	Size measured as >0 and ≤1	Size measured as >1 and ≤2	Size measured as >2	Necrosis or exfoliative dermatitis OR results in ER visit or hospitalization		

AE=adverse event; eDiary=electronic diary; ER=emergency room.

Table 14 Solicited Systemic AE Severity Grading Scale

Solicited	Severity Grade				
Systemic AE a	Grade 1	Grade 2	Grade 3	Grade 4	
Irritability	Mild; mild symptoms; clinical or diagnostic observations only; intervention not indicated; awareness of symptoms but easily tolerated.	Moderate; minimal local or noninvasive intervention indicated. Infant is definitely acting like something is wrong.	Severe or medically significant but not immediately life-threatening; hospitalization or prolongation of hospitalization indicated; disabling. Infant is extremely irritable or unable to do usual activities.	Life-threatening consequences; urgent intervention indicated.	
Drowsiness	Mild; asymptomatic or mild symptoms; clinical or diagnostic observations only; intervention not indicated; awareness of symptoms but easily tolerated.	Moderate; minimal local or noninvasive intervention indicated. Infant is definitely acting like something is wrong.	Severe or medically significant but not immediately life-threatening; hospitalization or prolongation of hospitalization indicated; disabling. Infant is extremely distressed or unable to do usual activities.	Life-threatening consequences; urgent intervention indicated.	

<sup>a Based upon information provided by the legally acceptable representative in the eDiary and verbally during the eDiary review. Erythema/redness and swelling are specific injection-site AEs with size designations of numbers 1 through 8, as indicated on the study-supplied ruler. If the participant has an ER visit or is hospitalized for any injection-site AE, that AE is to be assigned a grade of 4, regardless of the size measured.

Solicited	Severity Grade		sed Severity Grade			
Systemic AE a	Grade 1	Grade 2	Grade 3	Grade 4		
Irritability	Mild; mild symptoms; clinical or diagnostic observations only; intervention not indicated; awareness of symptoms but easily tolerated.	Moderate; minimal local or noninvasive intervention indicated. Infant is definitely acting like something is wrong.	Severe or medically significant but not immediately life-threatening; hospitalization or prolongation of hospitalization indicated; disabling. Infant is extremely irritable or unable to do usual activities.	Life-threatening consequences; urgent intervention indicated.		
Appetite lost	Mild; asymptomatic or mild symptoms; clinical or diagnostic observations only; intervention not indicated; awareness of symptoms but easily tolerated.	Moderate; minimal local or noninvasive intervention indicated. Infant is definitely acting like something is wrong.	Severe or medically significant but not immediately life-threatening; hospitalization or prolongation of hospitalization indicated; disabling. Infant is extremely distressed or unable to do usual activities.	Life-threatening consequences; urgent intervention indicated.		

AE=adverse event; eDiary=electronic diary.

Table 15 Elevated Temperature (Rectal) Severity Grading Scale

	Severity Grade			
	Grade 1	Grade 2	Grade 3	Grade 4
Elevated Temperature				
(°C) a	≥38.0 to <39.0	≥39.0 to <40.0	≥40.0	≥40.0
(°F) a	≥100.4 to <102.2	≥102.2 to <104.0	≥104.0 for ≤24 hours	≥104.0 for >24 hours

<sup>a Rectal temperature. Correction factors to adjust axillary temperatures for an equivalent rectal temperature are axillary temperature +2 degrees in Fahrenheit OR axillary temperature +1.1 degrees in Celsius.

<sup>a Based upon information provided by the legally acceptable representative in the eDiary and verbally during the eDiary review.

PROTOCOL/AMENDMENT NO.: 004-05

Table 16 AESI: Anaphylaxis/Hypersensitivity Severity Grading Scale

	Severity Grade				
AESI Term	Grade 1	Grade 2	Grade 3	Grade 4	
Anaphylaxis	Not applicable	Not applicable	Symptomatic bronchospasm, with or without urticaria; parenteral intervention indicated; allergy-related edema/angioedema; hypotension	Life-threatening consequences; urgent intervention indicated	
Angioedema	Mild; asymptomatic or mild symptoms; clinical or diagnostic observations only; intervention not indicated; awareness of symptoms, but easily tolerated	Moderate; minimal, local or noninvasive intervention indicated. Infant is definitely acting like something is wrong	Severe or medically significant but not immediately life-threatening; intensive intervention indicated; disabling. Infant is extremely distressed or unable to do usual activities	Life-threatening consequences; urgent intervention indicated	
Bronchospasm	Mild symptoms; intervention not indicated	Symptomatic; medical intervention indicated; limiting routine activities such as feeding	Limiting routine activities such as feeding; supplemental oxygen indicated	Life-threatening respiratory or hemodynamic compromise; intubation or urgent intervention indicated	
Drug hypersensitivity (drug-related allergic reaction)	Allergic reaction; systemic intervention not indicated	Oral intervention indicated	Bronchospasm; hospitalization indicated for clinical sequelae; IV intervention indicated	Life-threatening consequences; urgent intervention indicated	
Hypersensitivity	Allergic reaction; systemic intervention not indicated	Oral intervention indicated	Bronchospasm; hospitalization indicated for clinical sequelae; IV intervention indicated	Life-threatening consequences; urgent intervention indicated	
Dyspnea (difficulty breathing)	Shortness of breath with moderate exertion	Shortness of breath with minimal exertion; limiting routine activities such as feeding	Shortness of breath at rest; limiting routine activities such as feeding	Life-threatening consequences; urgent intervention indicated	
Dysphonia	Mild sore throat; raspy voice	Moderate sore throat; analgesics indicated	Severe throat pain; endoscopic intervention indicated	Not applicable	
Wheezing  AESI-adverse eve	Detectable airway noise with minimal symptoms  ent(s) of special interest.	Moderate symptoms; medical intervention indicated; limiting routine activities such as feeding	Severe respiratory symptoms limiting routine activities such as feeding; oxygen therapy or hospitalization indicated	Life-threatening consequences; urgent intervention indicated	

PROTOCOL/AMENDMENT NO.: 004-05

Table 17 AESI: Rash Severity Grading Scale

	Severity Grade				
AESI Term	Grade 1	Grade 2	Grade 3	Grade 4	
Acute generalized exanthematous pustulosis (AGEP)	Not applicable	Not applicable	Severe or medically significant but not immediately life-threatening; hospitalization or prolongation of existing hospitalization indicated; limiting routine activities such as feeding	Life-threatening consequences; urgent intervention indicated	
Drug eruption	Lesions covering <10% BSA; topical intervention indicated	Lesions covering 10–30% BSA; oral intervention indicated	Lesions covering >30% BSA; IV intervention indicated	Not applicable	
Drug reaction with eosinophilia and systemic symptoms (DRESS)	Not applicable	Not applicable	Severe or medically significant but not immediately life-threatening; hospitalization or prolongation of existing hospitalization indicated; limiting routine activities such as feeding	Life-threatening consequences; urgent intervention indicated	
Erythema multiforme	Target lesions covering <10% BSA and not associated with skin tenderness	Target lesions covering 10-30% BSA and associated with skin tenderness	Target lesions covering >30% BSA and associated with oral or genital erosions	Target lesions covering >30% BSA; associated with fluid or electrolyte abnormalities; ICU care or burn unit indicated	
Generalized rash of exfoliative nature (including dermatitis exfoliative and exfoliative rash)	Not applicable	Erythema covering >90% BSA without associated symptoms	Erythema covering >90% BSA with associated symptoms (eg, pruritus or tenderness); limiting routine activities such as feeding	Erythema covering >90% BSA with associated fluid or electrolyte abnormalities; ICU care or burn unit indicated	
Stevens-Johnson syndrome	Not applicable	Not applicable	Skin sloughing covering <10% BSA with associated signs (eg, erythema, purpura, epidermal detachment, and mucous membrane detachment)	Skin sloughing covering 10–30% BSA with associated signs (ie, erythema, purpura, epidermal detachment, and mucous membrane detachment)	

PRODUCT: MK-1654

PROTOCOL/AMENDMENT NO.: 004-05

	Severity Grade			
AESI Term	Grade 1	Grade 2	Grade 3	Grade 4
Toxic epidermal necrolysis	Not applicable	Not applicable	Not applicable	Skin sloughing covering ≥30% BSA with associated symptoms (eg, erythema, purpura, or epidermal detachment)
Urticaria (hives or welts)	Urticarial lesions covering <10% BSA; topical intervention indicated	Urticarial lesions covering 10-30% BSA; oral intervention indicated	Urticarial lesions covering >30% BSA; IV intervention indicated	Not applicable
AESI=adverse event(s) of special interest; BSA=body surface area; ICU=intensive care unit; IV=intravenous.				

C Confidential

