#### **Medical Conditions**

- 2. Has known hypersensitivity to any component of MK-1654 (refer to the IB for a list of components).
- 3. Has a bleeding disorder contraindicating intramuscular administration.
- 4. Has had a recent illness with rectal temperature ≥100.5°F (≥38.1°C) or axillary temperature ≥100.0°F (≥37.8°C) within 72 hours predose.
  Note: If the participant meets this exclusion criterion, the participant may be rescreened when this criterion is not met.

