## **8.3.3** Body Temperature Measurement

Rectal or axillary temperature will be taken by study staff predose and after the 30-minute postdose safety observation period at Visit 1 and at all scheduled and unscheduled visits postdose, as indicated in the SoA (Section 1.3).

Rectal is the preferred method of obtaining participant's temperature and should be performed unless prohibited by local authorities or local pediatric guidelines. Axillary (underarm) is an acceptable method. Use of oral, temporal, or tympanic thermometers to collect temperature for this study is **not** permitted.

Additionally, the participant's legally acceptable representative will be asked to record a temperature reading and method of measurement (rectal\* or axillary) in the eDiary on Days 1 through 5 postdose. Temperature readings should be taken at approximately the same time each day with the thermometer provided by the study.

\*Note: For legally acceptable representatives unfamiliar with how to take a rectal temperature, site staff should provide training.

If an elevated temperature is detected using the axillary method ( $\geq 100.0^{\circ}F$  [ $\geq 37.8^{\circ}C$ ]), the temperature should be confirmed by rectal measurement (unless prohibited by local authorities or local pediatric guidelines). If rectal measurement is prohibited, a repeat axillary temperature measurement should be obtained.

Fever is defined as any rectal temperature  $\geq 102.2^{\circ}F$  ( $\geq 39.0^{\circ}C$ ) or axillary temperature  $\geq 101.7^{\circ}F$  ( $\geq 38.7^{\circ}C$ ). All fevers must be reported for Days 1 through 42 unless the fever is a symptom of another reported AE. If a temperature is recorded in the eDiary that meets this definition of fever, the site should call the legally acceptable representative to inquire about respiratory symptoms or any other symptoms. If no other symptoms are present, the fever should be reported as an AE.

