# 9.4.2 Safety Endpoints

Safety and tolerability of MK-1654 in this study will be assessed by clinical review of all relevant parameters including AEs and laboratory values. The endpoints that will be used to assess the safety and tolerability of MK-1654 include the following:

- Number of participants experiencing solicited injection-site AEs (redness/erythema, swelling, and pain/tenderness) from Days 1 through 5 postdose
- Number of participants experiencing solicited daily body temperature, with fever defined as rectal temperature ≥102.2°F (≥39.0°C) or axillary temperature ≥101.7°F (≥38.7°C), from Days 1 through 5 postdose
- Number of participants experiencing solicited systemic AEs (irritability, drowsiness, and appetite lost) from Days 1 through 5 postdose
- Number of participants with anaphylaxis/hypersensitivity AESI from Days 1 through 42 postdose

- Number of participants with rash AESI from Days 1 through 42 postdose
- Number of participants experiencing nonserious AEs occurring from Days 1 through 42 postdose
- Number of participants experiencing SAEs through the duration of study participation (from the time the consent form is signed through completion of the participant's participation in the study; for complete details on SAE data collection, see Section 10.3.5).

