#### **Tier 2 Events**

Membership in Tier 2 requires that at least 1% participants in any treatment group exhibit the event; OR AEs listed in Table 7. All other AEs will belong to Tier 3. Maximum body temperature will be summarized using Brighton Collaboration cutoffs.

The threshold of at least 1% was chosen to draw clinical meaningful inference. When less than 1% of participants report AEs in both groups, the 95% CI for the between-group difference may exclude zero. However, the clinical significance of these differences is unknown given the small number of participants who report AEs. Because many 95% CIs for Tier 2 events may be provided without adjustment for multiplicity, the CIs should be regarded as a helpful descriptive measure to be used in review, not a formal method for assessing the statistical significance of the between-group differences in AEs.

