#### **Assessment of severity**

- An event is defined as "serious" when it meets at least 1 of the predefined outcomes as described in the definition of an SAE, not when it is rated as severe.
- The investigator will assess the severity for each AE, SAE, and AESI (and other reportable safety event) reported during the study. Severity will be graded according to an adaption of NCI CTCAE version 5.0 as applicable for pediatric assessments. Where necessary, the NCI CTCAE scale has been adapted to conform to AE assessment for infant participants. Once the assessment has been made, the severity grade should be recorded in the "overall toxicity grade" section of the AE eCRF.

PROTOCOL/AMENDMENT NO.: 004-05

The severity of solicited injection-site AEs, solicited systemic AEs, elevated temperature, and AESI will be assessed according to the grading criteria (for Grade 1 through Grade 4) provided in Table 13 through Table 17. Additional grading definitions for AEs are provided in the separate study document: Severity Grading for Adverse Events.

- The severity for all other types of AEs that are not in the adapted NCI CTCAE will be determined by the investigator based upon clinical judgment and by using the following severity grading criteria (for Grade 1 through Grade 4):
  - **Grade 1**: Mild; mild symptoms; clinical or diagnostic observations only; intervention not indicated; awareness of symptoms, but easily tolerated.
  - Grade 2: Moderate; minimal, local, or noninvasive intervention indicated. Infant is definitely acting like something is wrong.
  - **Grade 3**: Severe or medically significant but not immediately life-threatening; intensive intervention indicated; disabling. Infant is extremely irritable or unable to do usual activities.
  - **Grade 4**: Life-threatening consequences; urgent intervention indicated.
  - Any AE that results in death will be assigned a severity grade of Grade 5.

It is important to distinguish between seriousness criteria and severity of an AE. Severity is a measure of intensity whereas seriousness is defined by the criteria in Section 10.3.3. A Grade 3 AE is not necessarily considered an SAE. For example, a Grade 3 headache that persists for several hours may not meet the definition of an SAE and would be considered a nonserious event, whereas a Grade 2 seizure resulting in a hospital admission would be considered an SAE.

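### Table 15 adds 1.1°C to axillary readings, but the paired fever cut-offs differ by only 0.3°C, so an axillary-only reading of 37.9–38.6°C is Grade 2 yet not a fever

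*Combined protocol and SAP*

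**What the plan says.** Fever is part of a primary safety endpoint. Section 9.4.2, in line with Sections 3 and 8.3.3, has "fever defined as rectal temperature ≥102.2°F (≥39.0°C) or axillary temperature ≥101.7°F (≥38.7°C), from Days 1 through 5 postdose". Exclusion criterion 4 (Section 5.2) uses a second pair for recent illness: "rectal temperature ≥100.5°F (≥38.1°C) or axillary temperature ≥100.0°F (≥37.8°C) within 72 hours predose".

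Severity follows a separate route. Section 10.3.5 states: "The severity of solicited injection-site AEs, solicited systemic AEs, elevated temperature, and AESI will be assessed according to the grading criteria", and points to Tables 13 to 17. Table 15 is on the rectal scale. Its Grade 2 band is "≥39.0 to <40.0" in Celsius and "≥102.2 to <104.0" in Fahrenheit. Its footnote gives the correction for axillary readings: "axillary temperature +2 degrees in Fahrenheit OR axillary temperature +1.1 degrees in Celsius".

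Section 8.3.3 prefers rectal measurement but accepts axillary. An axillary reading of 37.8°C or more is to be confirmed rectally unless local rules forbid it. For that case: "If rectal measurement is prohibited, a repeat axillary temperature measurement should be obtained". The caregiver records the method with each reading in the eDiary.

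Section 9.6.2 adds: "Maximum body temperature will be summarized using Brighton Collaboration cutoffs". It does not say how axillary readings enter that summary.

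**The concern.** The document uses two different relationships between the routes. Both cut-off pairs place axillary 0.3°C below rectal; the footnote, which is the only stated conversion, places it 1.1°C below. Nothing in the text reconciles them.

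The consequence depends on which relationship is meant:

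- If 1.1°C is the true equivalence, the axillary fever cut-off of 38.7°C corresponds to rectal 39.8°C, and fever is under-counted where only axillary readings exist.
- If the 0.3°C pairing is the true equivalence, fever counts are comparable across routes, but axillary grades are shifted upwards.

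Either way, fever status and grade for axillary-only readings do not share one scale with rectal readings. Because prohibition of rectal measurement depends on local authorities or guidelines, such readings would tend to cluster by locality, and pooled fever rates and grades would mix two scales.

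**Working it through.** **Inputs.** Fever cut-offs from Section 9.4.2; recent-illness cut-offs from Section 5.2; grade bands and correction from Table 15; the 37.8°C confirmation threshold from Section 8.3.3.

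**Gap implied by each pair (rectal minus axillary).**

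- Fever: 39.0 − 38.7 = 0.3°C; 102.2 − 101.7 = 0.5°F.
- Recent illness: 38.1 − 37.8 = 0.3°C; 100.5 − 100.0 = 0.5°F.
- Table 15 footnote: 1.1°C; 2°F.

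**Units and rounding do not explain it.** 2°F / 1.8 = 1.11°C, which agrees with 1.1°C. 0.5°F / 1.8 = 0.28°C, which agrees with 0.3°C. Each rule is consistent across units; the two rules differ from each other.

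**Where Grade 2 starts relative to fever.** For rectal readings, Grade 2 starts at 39.0°C (102.2°F), which is exactly the fever cut-off. For axillary readings under the footnote, it starts at 39.0 − 1.1 = 37.9°C, and 38.7 − 37.9 = 0.8°C below the axillary fever cut-off.

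**Grades under each relationship.** Table 15 bands on the rectal scale: Grade 1 from 38.0 to below 39.0°C, Grade 2 from 39.0 to below 40.0°C, Grade 3/4 from 40.0°C (split by duration).

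| Axillary °C | +1.1°C | Grade | +0.3°C | Grade | Fever (axillary ≥38.7°C) |
|---|---|---|---|---|---|
| 37.8 | 38.9 | 1 | 38.1 | 1 | No |
| 37.9 | 39.0 | 2 | 38.2 | 1 | No |
| 38.6 | 39.7 | 2 | 38.9 | 1 | No |
| 38.7 | 39.8 | 2 | 39.0 | 2 | Yes |
| 38.8 | 39.9 | 2 | 39.1 | 2 | Yes |
| 38.9 | 40.0 | 3/4 | 39.2 | 2 | Yes |
| 39.6 | 40.7 | 3/4 | 39.9 | 2 | Yes |
| 39.7 | 40.8 | 3/4 | 40.0 | 3/4 | Yes |

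**Count.** From the confirmation threshold of 37.8°C to 39.6°C there are 19 steps of 0.1°C. The grades differ at 37.9–38.6°C (8 steps) and at 38.9–39.6°C (8 steps), so at 16 of 19. They agree at 37.8, 38.7 and 38.8°C, and again from 39.7°C upwards.

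**Fahrenheit.** Grade 2 starts at axillary 102.2 − 2 = 100.2°F or 102.2 − 0.5 = 101.7°F. Grade 3/4 starts at 104.0 − 2 = 102.0°F or 104.0 − 0.5 = 103.5°F. The conflicting bands are 100.2–101.6°F and 102.0–103.4°F.

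**Below the confirmation threshold.** Axillary 36.9–37.6°C becomes 38.0–38.7°C (Grade 1) under +1.1°C, and 37.2–37.9°C (no grade) under +0.3°C. No rectal confirmation is called for there. This band is left out of the count above.

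**The case against.** The strongest reply is that nothing is strictly contradictory. The fever definition sets a cut-off for each route and never calls 0.3°C a conversion; the footnote is the only conversion, and both can be applied as written. A graded temperature that is not a fever is also built into Table 15, since all of rectal Grade 1 lies below the fever cut-off. This does not explain why rectal Grade 2 coincides with the rectal fever cut-off in both units while corrected axillary Grade 2 starts 0.8°C below its own cut-off.

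The count of 16 of 19 compares the written rule with a 0.3°C grading rule that is inferred from the pairs, and the range ends at the last discordant step. That is fair. Only the 8 steps at 37.9–38.6°C show Grade 2 without fever; the other 8 are fevers and at least Grade 2 either way. The count is not a share of readings or participants.

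Rectal confirmation removes much of the problem, since all 16 steps lie above its threshold. That also stands. What remains is readings where rectal measurement is prohibited and cases where confirmation was missed.

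Finally, fever status never uses Table 15, Table 7 lists no analysis by grade, and the Tier 2 intervals are descriptive. These points limit the consequence, but Section 10.3.5 still has investigators record the grade. The separate Severity Grading for Adverse Events document was not available; it might clarify the intent, but the protocol text would still conflict.

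**Conclusion.** The concern holds. The Table 15 correction of 1.1°C cannot be recovered from the protocol's own paired cut-offs, which imply 0.3°C. For axillary-only readings, 37.9–38.6°C is Grade 2 without being a fever, and 38.9–39.6°C is Grade 3/4 where the 0.3°C pairing gives Grade 2.

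The effect is on absolute fever rates and severity grades compared or pooled across routes. In a blinded randomized trial no directional difference between arms is expected. The number of participants affected cannot be estimated, because the axillary-only share is not given. Whether fever is under-counted or grades are inflated depends on which relationship the sponsor intends, and the documents do not settle that. It should be corrected, but it does not threaten the efficacy conclusions.

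**What to change.** Reconcile the Table 15 footnote with the paired fever cut-offs so that a single rectal–axillary relationship governs both fever status and grade. Which one is for the sponsor to decide. Then:

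- State whether the maximum-temperature summary in Section 9.6.2 uses the same relationship.
- State in Section 8.3.3 that a confirmatory rectal value, when present, is the one used. This is a clarification only.
- Bring the site grading instructions and the separate Severity Grading for Adverse Events document into line, since investigators assign the grades.
- As a check, tabulate fever and grades by the measurement route recorded in the eDiary.

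The cost is wording in one footnote and one section, a derivation rule, and matching site instructions. No new data are needed.
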